### 10.1.3 Assessment of Severity

The intensity of the complication will be rated as mild, moderate, or severe using the following criteria:

- **Mild:** These events require minimal or no treatment and do not interfere with the subject’s daily activities.
- **Moderate:** These events result in a low level of inconvenience or concern with the therapeutic measures. Moderate events may cause some interference with functioning.
- **Severe:** These events interrupt a subject’s usual daily activity and may require systemic drug therapy or other treatment. Severe events are usually incapacitating.

Changes in the severity of a complication should be documented to allow an assessment of the duration of the event at each level of intensity to be performed.

## 10.2 Serious Complications

### **10.2.1 Definition and documentation of serious complications**

In compliance with ICH-GCP (guideline E6 [R2]) section 4.11 and 5.17 we have taken the decision that the documentation and expedited reporting should be limited to events showing a causal relationship to the study procedure. For this reason, the investigator is obliged to document only the following events:

- Death of the patient,
- Life-threatening situation (patient is at immediate risk of death),
- Persistent or significant disability/incapacity.

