### 2.3 Secondary endpoints

Risk of falling at 12 months will be defined as in 2.2 within 12 months.

Injurious falls (total number) are subdivided by “moderate” and “serious” [48]:

- 1) Moderate injurious falls are defined as those that resulted in sprains, bruises, scrapes, or joint injuries or if the individual needed medical care
- 2) Serious injurious falls are defined as those that resulted in a fracture, head injury, tendon rupture, or admission to a hospital (inpatient care), or that required stitches.

The BBS is a 14-item scale primarily assessing standing balance and sit-to-stand positions. Scores are based on a 5-point scale, rating from 0 to 4, based on performance quality and duration, or assistance needed. “0” indicates the lowest and “4” the highest level of function. The total score ranges from 0 to 56 points [50].

The MoCA is a brief cognitive screening tool for mild cognitive impairment and assesses several cognitive domains. The total sum score ranges from 0 to 30 and higher scores indicate higher functioning [51].

The Short FES-I is a 7-item questionnaire to measure fear of falling in elderly patients during different activities. It is to be filled out by the patient him/herself. Each item is rated on a four-point scale from 1 (not at all concerned) to 4 (very concerned). The total score ranges from 7 (no concern about falling) to 28 (severe concern about falling) [49].

The GDS-15 is a short, 15-item instrument, developed and validated for measurement of depressive symptoms among elderly people. It is to be filled out by the patient him/herself. Its items require a yes/no response. The total score ranges from 0 to 15. Sum scores 0-4 are considered normal, sum scores 12-15 indicate severe depression, in between as mildly depressed [52].

The SF-12 is a short-form generic measure of health status from the patient’s point of view. It is to be filled out by the patient him/herself. It contains 12 items on 8 health concepts. Results are expressed in terms of two meta-scores: Physical Component Summary and Mental Component Summary. Scores range from 0 to 100. Higher scores indicate better functioning. The mean score in a representative sample of the US population is 50 [53].

The IADL evaluates complex instrumental activities of daily living, on 8 items. The total score ranges from 0 to 8 in women, and from 0 to 5 in men [54].

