## 10 Safety monitoring and reporting

### 10.1 Complications

#### 10.1.1 Definition of complications

Only complications that could arise from the study specific intervention (EYT or Tai Chi or other exercises in the standard care group) will be collected, documented and – in case of serious complications – reported to the Data Monitoring Committee, DMC (details see chapter 10.3 and DMC Charter). A complication in the ENTAiER study is defined as any untoward medical occurrence in a trial patient such as any unfavourable and unintended sign, symptom, or disease that is possibly related to the study intervention. As the (non-pharmacological) intervention (EYT and Tai Chi) is training of musculoskeletal, sensory, concentrative elements, complications can be:

- Injuries caused by falls that happened during exercises in groups or at home.
- Musculoskeletal pain – except aching muscle - (e.g. foot, knee, low back pain, arthritis, joint effusion, reduced joint function), neuralgia, cardiovascular disorders (e.g. dizziness or faintness, symptoms of hypotension or hypertension, syncope, chest pain, cardiac arrhythmia), vertigo, dizziness, fatigue, syncope, dyspnoea, bronchospasm, dyspnoea, neurological cognitive disturbance, confusion, mood alteration, or others.

Not regarded as complications are

- conditions that were already present at the time of informed consent  
aching muscle ('Muskelkater'), which is to be expected.

The expression "related" means, that there is evidence or argument to suggest a reasonable causal relationship between the event and the administration of the intervention, e.g. close temporal connection, exclusion of other causes.

The assessment "not related" is appropriate, if the complication is clearly or most likely explained by other causes even if a potential relationship between treatment and the complication cannot be completely excluded.

Falls and injurious falls will be documented as primary outcomes. In case they happen during exercises in groups or at home, this will be noted. They will also be reported to the study center by therapists or teachers in case that they happen during exercises. Injuries caused by falls that happened during exercises in groups or at home will be documented as complications and indicated as caused by a fall. All falls that happen during exercises in groups or at home will be reported to the DMC with the regular report on complications.

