### 10.1.2 Documentation of complications

All such complications as defined in 10.1.1 reported by the patient or observed by the investigator, teacher or therapists will be continuously documented in the designated case report form (Complications form) during the clinical trial/at each follow-up visit.

Patients will be asked using open questions regarding their condition and any untoward medical occurrences during the last four weeks or any unplanned visits to a doctor, ambulance or hospital. In case of an occurrence, causal relationship with the study intervention EYT or Tai Chi, or, for instance in case of patients allocated to standard care alone, with physical training will be assessed.

In case of a potential causal relation to the intervention, the complication has to be documented in the CRF starting from the first administration and until at least 7 days after the last administration of the intervention.

Following information will be documented:

- Characterization of the event
- Onset date, if available
- Severity: see “assessment of severity” (see Section 10.1.3))
- Serious or non-serious
- Action taken with Intervention
- Outcome

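### The list of serious complications in 10.2.1 omits related hospital admission and fracture, so an exercise fall that 2.3 calls serious can be flagged non-serious for safety

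*Protocol*

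**What the plan says.** Three parts of the protocol bear on the same event.

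- **Safety definition (10.2.1).** The section introduces its list with "the investigator is obliged to document only the following events". The list has three entries, ending with "Persistent or significant disability/incapacity". The clarification that follows explains how to read life-threatening and death, and adds no further criterion. The reason given is that documentation and expedited reporting are confined to events causally related to the study procedure.
- **Outcome definition (2.3).** "Serious injurious falls are defined as those that resulted in a fracture, head injury, tendon rupture, or admission to a hospital (inpatient care"; injuries needing stitches are counted as well.
- **Link between the two (10.1.1 and 10.1.2).** "Injuries caused by falls that happened during exercises in groups or at home will be documented as complications", and each complication carries the entry "Serious or non-serious".

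On reporting, 10.1.1 has complications "in case of serious complications – reported to the Data Monitoring Committee, DMC", and refers for details to chapter 10.3 and the DMC Charter. It adds: "All falls that happen during exercises in groups or at home will be reported to the DMC with the regular report on complications".

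**The concern.** Causality and seriousness are separate criteria. Confining safety reporting to related events is a stated choice and can be defended. It does not lead to the list that follows, because an admission judged to be caused by the exercise meets the causality condition and is still left out.

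The omission touches a plausible harm. Participants are selected for a Berg Balance Scale score of 49 or less, and section 1.3 names fall injuries and fractures during sessions among the harms reported in exercise trials. It also reaches beyond falls: 10.1.1 lists syncope, chest pain and arrhythmia as possible complications, and a related admission for any of these would be non-serious too.

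At stake are the count of serious complications that supports the safety conclusion, and the class of events that 10.1.1 singles out for the DMC. Under section 7.1 the DMC supports the decision whether to stop an arm.

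**Working it through.** **1. Definitions side by side.** Take a patient who falls in a group session, fractures a wrist, is admitted, and recovers without lasting disability.

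| Section | Question | Result |
|---|---|---|
| 2.3 | Serious injurious fall? | Yes, on two criteria (fracture, admission) |
| 10.1.1 | Complication? | Yes, injury from a fall during exercise |
| 10.2.1: death | Met? | No |
| 10.2.1: life-threatening | Met? | No |
| 10.2.1: disability | Met? | No |
| 10.1.2 | Flag | Non-serious |

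A related admission for arrhythmia without a fall gives the same flag. If the fracture leaves persistent or significant disability, the third criterion is met and the flag becomes serious. The gap is thus confined to fractures and admissions without life threat or such disability.

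**2. Direction.** Adding criteria to a list can only keep or raise the number of events that meet it. The serious count under 10.2.1 is therefore at most the count under a list that includes admission and fracture.

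**3. Reporting route.** The section 10 headings end at 10.2.2 and section 11 follows, in both the table of contents and the text, so there is no chapter 10.3. Section 10.2.1 mentions expedited reporting, but 10.2.2 asks only for entry in the eCRF. The protocol itself gives no time limit for expedited reporting.

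**4. Size.** The protocol states no expected number, so there is none to reproduce. The following is an illustration. Inputs:

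- 550 patients randomised 1:1:1 (14.3), so 550 × 2/3 ≈ 367 in the two exercise arms.
- 24 + 12 = 36 sessions (8.1: twice weekly for 12 weeks, then weekly for 12 weeks).
- A cited Tai Chi trial: 2 falls during classes in 85 adults over 48 classes (1.3).
- 5% of falls lead to a fracture (1.1).

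Assume that this in-class fall rate applies to both exercise arms and that the general fracture share applies to in-class falls.

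- In-class falls = 367 × 2/85 ≈ 8.6. Scaled to 36 of 48 sessions: 8.6 × 36/48 ≈ 6.5.
- In-class fractures = 5% of these: 0.05 × 6.5 ≈ 0.32 and 0.05 × 8.6 ≈ 0.43.
- Chance of at least one = 1 − exp(−expected): 1 − exp(−0.32) ≈ 28% and 1 − exp(−0.43) ≈ 35%.

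One reclassified event would be 1/367 ≈ 0.27% of the exercise patients. Falls during home practice and admissions without a fall are not in these figures, and the protocol gives no rate for either.

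**The case against.** The best defence is that these are two constructs. Section 2.3 grades injury for an efficacy endpoint, with a definition taken from a cited trial. Section 10.2.1 sets a threshold for safety reporting. Nothing in the protocol requires them to match, and matching them fully would turn a stitched cut into a serious complication. The last point stands and limits the fix. The rest does not remove the problem: 10.1.1 and 10.1.2 send the same injury through both definitions, and the reason given in 10.2.1 does not account for the missing admission criterion.

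Four stronger readings are tempting, and the documents do not support them.

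- *Every in-class fracture with admission is non-serious.* A disabling one qualifies under 10.2.1.
- *These events go unrecorded or are hidden from the DMC.* They are documented as complications with severity and outcome, counted as serious injurious falls, and ascertained monthly. All exercise falls go into the DMC's regular report. Admissions are also collected through the health-care utilisation questionnaire (FIMA).
- *A planned rate of serious harm is biased.* Section 14.5.2 plans rates of complications and names no separate serious rate. Only results split by the flag are affected.
- *There is no route to the DMC.* The DMC Charter, which is not at hand, may set out the route and timing. What can be shown is that the pointer to 10.3 leads nowhere.

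**Conclusion.** The point holds within those limits. Followed exactly, the protocol would flag as non-serious a related admission or exercise-related fracture that is neither life-threatening nor disabling, and would keep it out of the class singled out for DMC reporting. The direction is certain: the serious-complication count can only be too low relative to a list with admission and fracture, while the total complication rate is unchanged. The size is not given in the documents. Under the assumed in-class fall rate it is about 0.3 to 0.4 in-class fractures, with roughly a one-in-three chance of any. With so few events expected, the classification of a single one can decide whether the report shows any serious complication. This should be corrected, but it does not threaten the efficacy analysis.

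**What to change.** - Reconcile 10.2.1 with 2.3, so that an intervention-related complication leading to inpatient admission, and a fracture from a fall during exercise, are not classed as non-serious. Do not import every criterion of 2.3; stitches, for example, can stay out.
- State in 10.2.1 that relatedness and seriousness are judged separately.
- In 10.1.1, replace the reference to chapter 10.3 with the actual reporting route to the DMC, or cite the DMC Charter alone.

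A comparison of serious complications across all three arms should not be added as part of this change. The safety population in 14.4 requires attendance at a group session, so standard-care patients who attended none are outside it. Such a table would need that definition changed as well.

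The cost is a short amendment and a few additional serious-complication reports. Little new data collection is needed: 10.1.2 already has patients asked about unplanned hospital visits, and 6.4 already provides for monthly ascertainment of injuries and their severity.

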#### **Clarification of serious complications:**

NOTE: The term “life-threatening” in the definition of “serious” refers to an event/reaction in which the patient was at risk of death at the time of the event/reaction; it does not refer to an event/ reaction which hypothetically might have caused death if it were more severe,

Please note that “death” is usually an outcome of a complication and not a serious complication per se. Only in cases where the clinical circumstances before the death are unknown (i.e. patient died without a determinable cause of death), then the diagnosis “death” itself should be reported as a serious complication. In case of fatal outcome of an already-registered serious complication, a follow-up notification must be done.

### **10.2.2 Documentation of serious complications**

All serious complications that occur starting from the first intervention and until at least 7 days after the last intervention will be documented in the eCRF.

## 11 Data Monitoring Committee

An independent data monitoring committee (DMC) will be established with the members listed in the section “Responsibilities” of this trial protocol. The function of the DMC is to monitor the course of the study and if necessary to give a recommendation to the Coordinating Investigator and sponsor of the trial for discontinuation, modification or continuation of the study.

The underlying principles for the DMC are ethical and safety aspects for the patients. It is the task of the DMC to examine whether the continuation of this trial is still ethically justifiable, whether the safety of patients is ensured, and whether trial progress is acceptable. For this purpose, the DMC has to be informed regularly about patient recruitment, compliance, and safety. The DMC will also receive the corresponding reports. The composition and responsibilities of the DMC, the structure and procedures of its meetings, and its relationship to other key study team members will be laid down in a separate DMC charter.

## 12 Data Collection, Handling and Management

### 12.1 Data confidentiality

Information about trial patients will be kept confidential and managed under the applicable laws and regulations. Those regulations require a signed patient authorization informing the patient of the following:

- what protected health information (PHI) will be collected from patients in this trial;
- who will have access to that information and why;
- who will use or disclose that information;
- the rights of a research patient to revoke their authorization for use of their PHI.

All subject data will be captured in pseudonymised form.

The electronic data capture (EDC) system utilized in this trial uses built-in security features to encrypt all data for transmission in both directions, preventing unauthorised access to confidential participant information. Access to the system will be controlled by individually assigned user identification codes and passwords, made available only to authorised personnel who have completed prerequisite training.

### 12.2 Documentation of trial data

#### Documentation in electronic case report form (eCRF)

An electronic data capture (EDC) system will be used in this trial. The investigator will document all trial data in a trial-specific electronic case report form (eCRF), as timely as possible. Data entry and data corrections on e-forms are automatically tracked in the audit trail created by the EDC system.

Data corrections in the eCRF due to queries are performed by the responsible investigator, or designated person, as timely as possible.

### 12.3 Data management

The data management will be performed with REDCap™ Version 8.6.5, a fully web based remote data entry system based on web forms, which is developed and maintained by the REDCap Consortium ([contact]).

Details on data management (procedures, responsibilities, etc.) will be described in a data management manual prior to the trial. The Data Management Manual is a working document

which will be continuously updated and maintained during the trial, i.e. the performance of data management and any deviations from the first version of the data management manual will be documented therein as well. The technical specifications of the database will be described in a data description plan (in short “DDP”). Before any data entry is performed, the trial database and edit checks will be tested. Data entry personnel will not be given access to the trial until they have been trained. An audit trail provides a data history of which data were entered, changed or deleted, by whom and when.

Data will be regularly reviewed for completeness, consistency and plausibility. The checks to be programmed will be specified beforehand in a data validation plan (integrated in the DDP stated above). After running the check programs, the resulting queries will be sent to the investigator for correction or verification of the documented data. Data corrections will be entered directly into REDCap by the responsible investigator, or a designated person.

#### **12.4 Data coding**

Complications will be coded using Medical dictionary for regulatory activities (MedDRA) terminology.

## 13 Quality Assurance System

The sponsor / coordinating investigator is responsible for implementing and maintaining quality assurance and quality control systems with written Standard Operation Procedures (SOP) to ensure that trials are conducted and data are generated, documented (recorded), and reported in compliance with the protocol, GCP, and the applicable regulatory requirement(s).

During the study, quality control and quality assurance will be ensured through monitoring, auditing and supervision.

### 13.1 Quality Control (Clinical Monitoring)

Monitoring is performed by the CRAs of the CTU, Medical Center - University of Freiburg. Risk-based monitoring will be done according to ICH-GCP (R2) and standard operating procedures (SOP) to verify that patients' rights and wellbeing are protected, reported trial data are accurate, complete and verifiable from source documents. This monitoring also verifies that the trial is conducted in compliance with the currently approved protocol/amendment, with ICH-GCP (R2) and with the applicable regulatory requirements to ensure safety and integrity of clinical trial data.

The investigator will grant the CRA access to the patients' personal medical records for the verification of the proper documentation of study data and agrees that the CRA will visit the study site before, during and after completion of the study for the fulfilment of his/her duty. The investigator must allow sufficient time for these visits, alternatively the CRA may be provided with other trained staff (e.g. so-called co-investigators) for assistance during the visits.

During the trial, the CRA will visit the study site regularly depending on the recruitment rate and quality of data. During these on-site visits, the CRA verifies that the trial is conducted according to the trial protocol, trial specific procedures, ICH-GCP (R2) and national/local regulatory requirements. The presence of signed informed consents, eligibility of patients, primary endpoint and documentation/reporting of safety data (e.g. (serious) complications) will be verified by the CRA.

A monitoring report will be written on each visit. This will document the progress of the study and give an account of all problems that occurred (e.g. refusal of inspection).

Between visits, the responsible CRA will maintain regular contact with the study sites. Further detailed information on monitoring will be recorded in a monitoring manual.

### 13.2 Source Data Verification (SDV)

Source data verification will be performed in order to verify the accuracy and completeness of the entries on the electronic case report form (eCRF) by comparing them with the source data, and to ensure and increase the quality of the data. The investigators will afford the CRA access to the medical records for the performance of SDV. Further detailed information on monitoring will be recorded in a monitoring manual.

Source data as defined by ICH-GCP (R2) include data such as hospital records, clinical and office charts, laboratory notes, memoranda, patients' diaries or evaluation checklists, pharmacy dispensing records, recorded data from automated instruments, copies or transcriptions certified after verification as being accurate copies, microfiches, photographic negatives, microfilm or magnetic media, x-rays, and records kept at the pharmacy, at the laboratories and at medico-technical departments involved in the clinical study.

